12.6. Secondary Efficacy Variables

In addition to all the secondary efficacy endpoints previously described, all the variables described above for the assessment of the primary objectives are also considered as secondary efficacy variables when evaluated at other time points than Week 4 and Week 12.

In addition, three VMS weekly weighted scores, taking into account both the frequency and the severity of VMS, will be computed based on the diary data as:

- $[(2 \times \text{number of moderate VMS}) + (3 \times \text{number of severe VMS})]$ for baseline and post baseline visits if at least one moderate to severe VMS was recorded and zero otherwise.
- $[(1 \times \text{number of mild VMS}) + (2 \times \text{number of moderate VMS}) + (3 \times \text{number of severe VMS})]$ for baseline and post baseline visits if at least one mild to severe VMS was recorded and zero otherwise.
- $[(2 \times \text{number of moderate VMS}) + (3 \times \text{number of severe VMS})]$ if at least one moderate to severe VMS was recorded for baseline visits and $[(1 \times \text{number of mild VMS}) + (2 \times \text{number of moderate VMS}) + (3 \times \text{number of severe VMS})]$ for post baseline visits if at least one mild to severe VMS was recorded and zero otherwise.

Furthermore, the severity score will also be recomputed as $[((1 \times \text{number of mild VMS}) + (2 \times \text{number of moderate VMS}) + (3 \times \text{number of severe VMS})) / (\text{total number of mild + moderate + severe VMS})]$ if at least one mild to severe VMS is recorded during the day for baseline and post baseline visits.

In case of documented absence of moderate to severe VMS during the day, the daily severity score will be set to zero. These additional efficacy variables will be derived for every week between baseline and week 12 based on the respective 7-day periods. All VMS related secondary efficacy variables will be expressed as changes from baseline computed as the differences of the estimated values at week 1 to 12 and the baseline values.

The percentage of subjects with a CID in the weekly frequency of moderate to severe VMS at weeks 4 and 12 will be assessed according to Gerlinger et al. (31).

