The text on the additional statistical analysis of the daily severity score has been moved from Secondary Efficacy Variables to Primary Efficacy Variables : and now reads as follows: "The daily severity score as defined above will also be recomputed for post baseline weeks as $[((2 \times \text{number of moderate VMS}) + (3 \times \text{number of severe VMS})) / (\text{Total number of moderate + severe VMS})]$ if at least one moderate or severe VMS is recorded during the day."	
There are differences between the FDA and EMA regulatory requirements on the assessment of efficacy in the treatment of VMS. The EMA guidance only includes moderate and severe VMS in the primary analysis, while in the FDA guidance also mild VMS are taken into account.
 
Both analyses were included in the previous version of the protocol, although in different subsections. Because results of this study will be used for submission to the FDA as well as to the EMA, both analyses have now been placed in the same section of the protocol (Primary Efficacy Variables), to indicate that they are equally important.
	2. Study synopsis (Statistical Methods) 12.4 Primary Efficacy Analysis 12.6 Secondary Efficacy Analysis
Week and treatment by week interaction have been added as fixed factors in the MMRM.	These models factors are necessary to get the estimates of the primary endpoint.	2. Study synopsis (Statistical Methods) 12.5. Analysis of Primary Efficacy Variables
The number of subjects has been made more flexible throughout the protocol.	For operational purposes this multiple centre trial requires some flexibility in the number of patients in each study part and stratum.	Throughout the protocol
Study-specific description of the Safety, ITT and PP analysis sets	To clarify the definition of the different statistical populations	12.1 Statistical Populations
The text on blood sampling for exploratory research has been adapted	Updates have been made for clarification purposes.	10.3.4 Blood Sampling for Exploratory Research
The text on retainment of samples for optional additional analyses in Section 10.4.5 has been reworded and has also been added to section 10.3.5.	Updates have been made for clarification purposes.	10.3.5 Endocrine assessment for inclusion and monitoring of treatment compliance 10.4.5 Routine Clinical Laboratory Tests

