- An imputation of missing data (last observation carried forward [LOCF] or other)
- The modeling strategy [analysis of covariance (ANCOVA) instead of MMRM]
- Confounders (for example ethnicity, hysterectomized status)
- Populations studied (mITT, PP)
- Any combination of the above

In addition, all primary efficacy variables will be tabulated at baseline and at each post-baseline time point.

Secondary Efficacy Variables:

In addition to all the secondary efficacy endpoints previously described, all the variables described above for the assessment of the primary objectives are also considered as secondary efficacy variables when evaluated at other time points than Week 4 and Week 12.

In addition, three VMS weekly weighted scores, taking into account both the frequency and the severity of VMS, will be computed based on the diary data as:

- $[(2 \times \text{number of moderate VMS}) + (3 \times \text{number of severe VMS})]$ for baseline and post baseline visits if at least one moderate to severe VMS was recorded and zero otherwise.
- $[(1 \times \text{number of mild VMS}) + (2 \times \text{number of moderate VMS}) + (3 \times \text{number of severe VMS})]$ for baseline and post baseline visits if at least one mild to severe VMS was recorded and zero otherwise.
- $[(2 \times \text{number of moderate VMS}) + (3 \times \text{number of severe VMS})]$ if at least one moderate to severe VMS was recorded for baseline visits and $[(1 \times \text{number of mild VMS}) + (2 \times \text{number of moderate VMS}) + (3 \times \text{number of severe VMS})]$ for post baseline visits if at least one mild to severe VMS was recorded and zero otherwise.

Furthermore, the severity score will also be recomputed as $[((1 \times \text{number of mild VMS}) + (2 \times \text{number of moderate VMS}) + (3 \times \text{number of severe VMS})) / (\text{total number of mild + moderate + severe VMS})]$ if at least one mild to severe VMS is recorded during the day for baseline and post baseline visits.

In case of documented absence of VMS during the day, the daily severity score will be set to zero. These additional efficacy variables will be derived for every week between baseline and week 12 based on the respective 7-day periods. All VMS related secondary efficacy variables will be expressed as changes from baseline computed as the differences of the estimated values at week 1 to 12 and the baseline values.

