12.4. Primary Efficacy Variables

The weekly frequency of moderate to severe VMS at baseline, week 4 and week 12, respectively, is defined as the total number (sum) of all recorded moderate to severe VMS experienced during the last 7 consecutive days during the Screening period, days 22 to 28 (week 4) and days 78 to 84 (week 12), respectively.

The mean severity score of VMS is defined as the arithmetic mean of the daily severity score values of VMS (moderate or severe) observed from days -7 to -1 at baseline and the arithmetic mean of the daily severity score values of VMS (mild, moderate or severe) observed during the days 22 to 28 and days 78 to 84 for week 4 and week 12 respectively.

At baseline, the daily severity score is computed as $[(2 \times \text{number of moderate VMS}) + (3 \times \text{number of severe VMS})] / (\text{total number of moderate + severe VMS})$ if at least one moderate to severe VMS was recorded during the day. In case of documented absence of moderate to severe VMS during the day, the daily severity will be set to zero.

Post-baseline (days 22 to 28 [Week 4] and days 78 to 84 [Week 12]), the daily severity score is computed as $[(1 \times \text{number of mild VMS}) + (2 \times \text{number of moderate VMS}) + (3 \times \text{number of severe VMS})] / (\text{total number of mild + moderate + severe VMS})$ if at least one mild to severe VMS was recorded during the day. In case of documented absence of VMS during the day, the daily severity will be set to zero.

The daily severity score as defined above will also be recomputed for post baseline weeks as $[(2 \times \text{number of moderate VMS}) + (3 \times \text{number of severe VMS})] / (\text{total number of moderate + severe VMS})$ if at least one moderate or severe VMS is recorded during the day.

The primary efficacy variables will be expressed as the changes from baseline computed as the differences between the estimated values at week 4 or 12 and the baseline values.

The analysis including the mild VMS will be used for submission to the FDA, the analysis without the mild VMS will be used for submission to the EMA.

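### Protocol 12.6 zeroes the mild-inclusive daily severity score on mild-only days, against its own formula and the Synopsis; the EMA severity score needs a matching clarification for the same days

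*Protocol*

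**What the plan says.** **Mild-inclusive secondary score.** Protocol 12.6 recomputes daily severity with mild VMS in numerator and denominator, weighted 1, 2 and 3 for mild, moderate and severe. The formula applies "if at least one mild to severe VMS is recorded during the day for baseline and post baseline visits". The next sentence reads "In case of documented absence of moderate to severe VMS during the day, the daily severity score will be set to zero". The Synopsis (Secondary Efficacy Variables) gives the same formula but closes with "In case of documented absence of VMS during the day, the daily severity score will be set to zero".

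**Primary severity scores.** Protocol 12.4 defines three daily scores:

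- Baseline, moderate and severe only, with its own zero rule: "In case of documented absence of moderate to severe VMS during the day, the daily severity will be set to zero".
- Post-baseline including mild (FDA), with its own zero rule: "In case of documented absence of VMS during the day, the daily severity will be set to zero".
- Post-baseline moderate and severe only, computed "if at least one moderate or severe VMS is recorded during the day". No zero rule follows, here or in the Synopsis. Section 12.4 adds that "the analysis without the mild VMS will be used for submission to the EMA".

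The supplied SAP covers only the Safety Study part and defines no VMS severity score. Its Introduction cites an Efficacy Study Part SAP version 3.0, which was not supplied.

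**The concern.** A day with mild VMS only is a documented diary day, and treatment may well produce such days. In 12.6 the formula and the sentence after it give that day different values, and the Synopsis sides with the formula. Two programmers working from different sections would produce different secondary results.

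The EMA score raises a related question. On a mild-only day its formula is 0/0. The zero rule just before it requires absence of all VMS, and the rule that would fit is written for baseline. This score supplies the week 4 and week 12 severity co-primary endpoints for the EMA, so its handling should be explicit before unblinding.

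**Working it through.** **Value of a day under each text**

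| Day | 12.6 formula | 12.6 zero sentence | Synopsis | EMA formula |
|---|---|---|---|---|
| No VMS | not applicable | 0 | 0 | not applicable |
| Mild only | 1 | 0 | 1 | 0/0 |
| Any moderate or severe | by formula | not applicable | by formula | by formula |

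Over every pattern of 0–2 mild, 0–2 moderate and 0–2 severe VMS, the 12.6 zero sentence and the Synopsis rule differ only on mild-only days. Each such day moves the weekly mean by 1/7 = 0.143.

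**One example week (assumed counts).** Four days have 2 mild, 2 moderate and 1 severe; three days have mild VMS only.

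- Mild-inclusive score on each of the four days: (2 + 4 + 3)/5 = 1.8. Weekly mean, Synopsis: (4 × 1.8 + 3 × 1)/7 = 1.457. Weekly mean, 12.6 zero sentence: (4 × 1.8)/7 = 1.029. The gap is 3/7 = 0.429.
- EMA score on each of the four days: (4 + 3)/3 = 2.333. With mild-only days as zero: (4 × 2.333)/7 = 1.333. With them left out: 2.333.

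**Difference between arms (illustration, E4 minus placebo; negative favours E4).** The plan states no figure that depends on this rule, so there is none to reproduce.

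- From the documents: entry at 50 VMS per week or more (8.2.1); phase 2 reductions of 65% on placebo and 84% on E4 15 mg, given without a time point (7.1.3.3).
- Assumed: mean baseline of 50/week; Poisson counts; 40% severe in both arms, so the mean EMA score on a scored day is 2 × 0.6 + 3 × 0.4 = 2.4; the mild rates below.
- Moderate/severe mean per day: 50/7 × 0.35 = 2.50 on placebo and 50/7 × 0.16 = 1.143 on E4. The probability p of a day with none is exp(-2.50) = 0.0821 and exp(-1.143) = 0.3189.

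Let q be the probability of a mild-only day. The 12.6 rule changes the arm difference by q(placebo) - q(E4).

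- Mild equal at 1/day: (1 - exp(-1)) × (0.0821 - 0.3189) = 0.632 × (-0.2368) = -0.15.
- Mild falling by 65%/84% from 1/day: 0.0821 × 0.295 - 0.3189 × 0.148 = 0.0242 - 0.0472 = -0.02. From 3/day: 0.0821 × 0.650 - 0.3189 × 0.381 = 0.0534 - 0.1215 = -0.07.
- Strong between-woman variation (gamma, shape 1): p = 1/(1 + mean) = 0.286 and 0.467. With proportional mild from 1/day and the same mild mean for every woman: 0.286 × 0.295 - 0.467 × 0.148 = +0.015. If mild counts share the woman's own factor, the change is -0.01 to -0.02 for 1 to 3 mild/day at baseline. If mild stays equal at 1/day: 0.632 × (0.286 - 0.467) = -0.11.

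For the EMA score, the zero rule gives 2.4 × (p(placebo) - p(E4)): 2.4 × (-0.2368) = -0.57 (Poisson), or 2.4 × (0.286 - 0.467) = -0.43 (gamma). If only mild-only days are unscored, the Poisson arm mean is 2.4 × (1 - p)/(1 - q):

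- Mild equal at 1/day: 2.4 × 0.6811/0.7984 - 2.4 × 0.9179/0.9481 = 2.047 - 2.324 = -0.28.
- Proportional from 1/day: 2.4 × 0.6811/0.9528 - 2.4 × 0.9179/0.9758 = 1.716 - 2.258 = -0.54. From 3/day: 1.861 - 2.327 = -0.47.
- Gamma with proportional mild, by simulation (200,000 women per arm): about -0.42 to -0.49 when mild counts also vary between women, and up to -0.52 when the mild mean is the same for all.

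**The case against.** The strongest reply concerns the EMA score. Section 12.4 recomputes a score already defined, and the identical moderate/severe formula at baseline carries a zero rule that fits mild-only days. The imputation rule in 12.3 is for missing diary information, which a mild-only day is not. No passage tells the analyst to leave documented days out. This stands: zero is the natural reading, and the gap is one of wording. It is still not stated, and of the three daily scores in 12.4 this is the only one without a zero rule.

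The 12.6 sentence may itself be the missing EMA rule. The Amendment 5 log records that "The text on the additional statistical analysis of the daily severity score has been moved from Secondary Efficacy Variables to Primary Efficacy Variables", so the sentence could have stayed behind when its formula moved. That is inference, but it would make both points one editorial leftover. The Efficacy Study Part SAP may also settle both. Neither reply removes the conflict between 12.6 and the Synopsis in the current protocol.

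A reader might infer more: that the 12.6 rule inflates the drug's effect, or that leaving days unscored necessarily works against it. Both hold in the illustration when mild rates are equal in the two arms. When mild VMS fall in proportion, the effects shrink, and both directions can reverse with between-woman variation. The documents give no mild rates by arm, so they support neither claim.

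**Conclusion.** Section 12.6 is wrong as written: its zero sentence contradicts its own formula and the Synopsis on mild-only days, by 1/7 of a point in the weekly mean per such day. It affects one additional secondary score. The EMA severity score lacks a stated value for the same days; that is a clarification, with zero the likely intent, and the unsupplied SAP may already give it.

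The size and direction of any effect on the E4–placebo difference are not known. The figures above show sensitivity to assumed mild rates, severe share and variation between women; they do not predict the trial's results. A reader might also infer that the EMA severity effect could vanish. That needs VMS-free days unscored as well, although the sentence before the EMA formula sets such days to zero, and it needs equal severe shares in both arms. The documents do not support it.

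The FDA severity score and the frequency endpoints are unaffected. Overall the point is minor.

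**What to change.** - In 12.6, replace the zero sentence for the mild-inclusive score with the Synopsis sentence, "In case of documented absence of VMS during the day, the daily severity score will be set to zero".
- In 12.4 and the Synopsis, add after the EMA formula the sentence already used for baseline, "In case of documented absence of moderate to severe VMS during the day, the daily severity will be set to zero", and make clear that it covers mild-only days.
- Before unblinding for the Visit 4 analysis, confirm that the Efficacy Study Part SAP states the same two rules.

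The cost is one sentence changed, one sentence added in two places, and one document check. No new data are needed.

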12.7. Analysis of Secondary Efficacy Variables

All VMS related secondary efficacy variables will be analyzed using the same methodology as for the primary efficacy variables and will be based on the data from the ITT population.

All other secondary continuous efficacy variables will be analyzed using either an ANCOVA or an MMRM model depending on the type of endpoint considered. These models will be evaluated using data from the ITT, PP and mITT populations without imputation of data. Appropriate covariates may be included in the analyses.

The other categorical efficacy variables (scores, responder analysis) will be analyzed using appropriate statistical methods for the comparison of each treatment arm to the placebo arm.

In addition, all secondary efficacy variables will be tabulated at baseline and at each post-baseline time point.

12.8. Safety parameters (safety set)

All safety parameters will be summarized using data from the Safety Analysis Set if not indicated otherwise. No formal statistical test will be performed to determine statistical significance between treatment groups. Continuous variables will be summarized using descriptive statistics (N, mean, standard deviation, median, minimum, maximum), categorical variables will be presented in frequency tables using counts and percentages. The frequency of endometrial events will be computed on the evaluable biopsies of the endometrium. The incidence of spotting/bleeding will be analyzed by a 28-day period. The incidence rate of endometrial events will be computed on the evaluable endometrium. The 95% two-sided CI will be computed on the observed frequency of hyperplasia/carcinoma of the endometrium.

12.9. Timing of analysis

The final analysis of the primary efficacy objective and the secondary efficacy objectives 1 and 2 of the Efficacy Study part will be triggered when all subjects in the Efficacy Study part have completed Visit 4 and will be conducted by an independent statistician. The analyses of all other efficacy and safety objectives from the Efficacy and Safety Study parts will be triggered when the overall end of the trial is reached (i.e. when all subjects in the Efficacy Study part have completed Visit 8). The efficacy endpoints and the safety endpoints of the Safety Study will be analyzed separately from those of the Efficacy Study at the end of the Safety Study.

A firewall group, composed of Estetra SRL representatives independent of the E4 project will be appointed. This group will have access to the unblinded data of final and interim analyses of the Efficacy Study part. Further details regarding the composition and role of the firewall group

will be provided in a charter. The clinical team, the subjects and the site and sponsor personnel involved in the clinical evaluation of the subjects will remain blinded of the treatment assignment in the Efficacy Study part until the end of the study.

The analyses to be done after completion of Visit 4 will be performed by an independent statistician. Only the overall outcome of the results will be provided to the clinical team. The clinical team, the subjects and the site and sponsor personnel involved in the clinical evaluation of the subjects will remain blinded of the treatment assignment until the end of the study. Blinding for the data at subject and treatment group levels will be kept through a firewall process that will be put in place. No individual listings with the subject numbers' information or tables per treatment group will be disseminated at the time of final or interim triggered analysis of the Efficacy Study part.

No changes in the study conduct will be undertaken regardless of the primary efficacy analysis results. The study will continue until its completion in order to contribute to the safety profile of the study medication.

13. ETHICS

13.1. Independent Ethics Committee/Institutional Review Board

Site initiations will be undertaken only after the IEC/IRB has given full approval of the study including approval for all study related documents according to GCP and applicable local regulatory requirements, and the sponsor has received a copy of this approval. This approval letter must be dated and must clearly identify the IEC/IRB and the documents being approved.

At the end of the study, the investigator (or sponsor where required) will notify the IEC/IRB about the study completion.

13.2. Ethical Conduct of the Study

This trial will be conducted in accordance with the Declaration of Helsinki, the ICH Guidelines for GCP and regulatory requirements as applicable. The Investigator agrees that the study will be conducted according to the protocol and these principles. The Investigator will conduct all aspects of this study in accordance with all national, state, and local laws of the pertinent regulatory authorities. Study documents will be maintained in accordance with applicable regulations. During the pre-trial activities, the investigator and his staff must have confirmed a working knowledge of the regulatory requirements of the clinical trial.

13.3. Compensation, Insurance, and Indemnity

Information regarding compensation, insurance, and indemnity will be provided to the Investigator in the Clinical Trial Agreement. Country-specific insurance will be obtained in accordance with local regulations.

13.4. Subject Information and Consent

The investigator is responsible for ensuring that the subject fully understands the nature and purpose of the trial. Each subject must give written consent according to local requirements after the nature of the study has been fully explained. The ICF(s) that is/are used must be approved by both the sponsor and by the reviewing IEC/IRB and be in a language that the subject can read and understand. The informed consent should be in accordance with principles that originated in the Declaration of Helsinki, current ICH and GCP guidelines, applicable regulatory requirements, and sponsor policy.

Subjects will be informed that their participation is voluntary and that they may withdraw consent to participate at any time without giving any reason. Subjects will be told that alternative treatments are available if they refuse to take part and that such refusal will not prejudice future treatment. The subject or legally acceptable representative will be given sufficient time to read the ICF and the opportunity to ask questions.

The ICFs and any subsequent amended ICFs, as well as any other written information provided to the subjects must be submitted for review to the EC/IRB and a favorable opinion must be received in advance of use. The ICF(s) must be signed before performance of any study-related activity. The original signed ICFs will be retained by the investigator and made available (for review only) to the trial monitor and auditor on request. Subjects will be given a signed copy of

the informed consent. Source documentation will also document that IC was obtained prior to study related activity.

The investigator is responsible for ensuring that the subject fully understands the nature and purpose of the trial. In general, information should be given in both oral and written form whenever possible. No subject should be obliged to participate in the trial. Subjects, their relatives, guardians (or if applicable legal representatives) must be given ample opportunity to inquire about the details of the trial. The information must make clear that refusal to participate or withdrawal from the trial at any stage is without any prejudice to any subsequent care. Subjects must be allowed sufficient time to decide whether or not they wish to participate.

The ICFs and any subsequent amended ICFs, as well as any other written information provided to the subjects must be submitted for review to the EC/IRB and a favorable opinion must be received in advance of use. Informed consent will be obtained prior to the conduct of any trial-related procedures. The original signed ICFs will be retained by the investigator and made available (for review only) to the trial monitor and auditor on request. Subjects will be given a signed copy of the informed consent. Source documentation will also document that IC was obtained prior to the subject's participation in the trial.

